### Study Protocol:

Following study enrolment (visit 1), each subject underwent a 75-g oral glucose tolerance test (OGTT). Participants who met the eligibility criteria were then continuously monitored for 72 hours (visit 2 to visit 3) with a retrospective continuous glucose monitoring (CGM) system (Medtronic, Northridge, CA). After 3 days of CGM (visit 3), the subjects were randomized (1:1) to receive either study group or control group for 4 weeks. Participants in the study group were instructed to replace breakfast with Glucerna SR (Abbot Nutrition) powder 52 g dissolved in 200 ml of warm water and both groups received lifestyle education. At the end of the 4-week intervention, subjects underwent another CGM from visit 4 (Day 29) to visit 5 (Day 32), at which a final OGTT in the fasting state was conducted. The schematic outline of study conduction is illustrated in the figure below.

The incremental area under the curve of postprandial blood glucose (AUCpp) during CGM was calculated as the area between the glucose concentration-time curve, and the pre-prandial baseline glucose value measured at 4 h after each meal. Intra-day glycaemic variability (GV) parameters include the standard deviation of blood glucose values (SDBG), glucose coefficient of variation (CV), and the mean amplitude of glycaemic excursions (MAGE). CV was calculated by dividing the SDBG by the mean of the corresponding glucose readings. MAGE was calculated as the arithmetic mean of the differences between consecutive peaks and nadirs. Only excursions of more than

1 SDBG of the mean glycaemic values were considered for the calculation of MAGE.

Anthropometric and biochemical parameters were measured at visit 1 (baseline) and visit 4 (post-intervention). Body mass index (BMI) was calculated as the weight (kg) divided by squared height (m). Blood pressure (BP) was measured twice using a standard mercury sphygmomanometer, and the average was documented. Venous blood samples were collected after an overnight fast. Biochemical parameters including fasting plasma glucose (FPG), 2-h plasma glucose (2h-PG) during OGTT, glycated haemoglobin A1c (HbA1c), glycated albumin (GA), insulin, triglycerides (TG), total cholesterol (TC), high density lipoprotein cholesterol (HDL-C), and low-density lipoprotein cholesterol (LDL-C) were assayed. Insulin sensitivity was evaluated by homeostasis model assessments of insulin resistance (HOMA-IR):  $\text{HOMA-IR} = \text{fasting insulin (in mU/L)} \times \text{FPG (in mmol/L)} / 22.5$ .

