### **Statistical analyses**

Continuous variables at baseline were compared between the two groups by Student's *t* test. Comparison of categorical variables between groups was performed by  $\chi^2$  tests. Differences in the parameters before and after treatment were analysed by paired *t* test. The changes ( $\Delta$ ) in variables were compared with Student's *t* test. Statistical analyses were performed using SPSS software version 17.0 (SPSS Inc., Chicago, IL, USA). A *P* value of  $< 0.05$  (two-tailed) was considered statistically significant.

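### Is the follow-up CGM taken on the breakfast regimen or after it, and does the visit given for 2h-PG change the analysis?

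*Combined protocol and SAP*

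**What the plan says.** All the timing information is in the Study Protocol section. Baseline CGM comes first; participants are "continuously monitored for 72 hours (visit 2 to visit 3"). Allocation follows: "After 3 days of CGM (visit 3), the subjects were randomized (1:1) to receive either study group or control group for 4 weeks". The follow-up recording is described as: "At the end of the 4-week intervention, subjects underwent another CGM from visit 4 (Day 29) to visit 5 (Day 32"), and the last glucose tolerance test is placed at "visit 5 (Day 32), at which a final OGTT in the fasting state was conducted".

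The measurements paragraph of the same section says: "Anthropometric and biochemical parameters were measured at visit 1 (baseline) and visit 4 (post-intervention"). Its list of assays opens with "Biochemical parameters including fasting plasma glucose (FPG), 2-h plasma glucose (2h-PG) during OGTT".

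The Statistical analyses section treats each variable as one value before and one value after: "Differences in the parameters before and after treatment were analysed by paired *t* test". Changes are then compared between arms by Student's *t* test. Nothing there refers to whether a participant is still on the product when the follow-up value is taken.

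**The concern.** Two things look wrong.

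First, only visits 4 and 5 carry day numbers in the readable text, and Day 1 is not tied to a visit. Only breakfast is replaced, so a direct product effect on the post-meal area under the curve (AUCpp) can arise only at breakfasts where the product is taken. If the follow-up CGM days are on the regimen, the changes in AUCpp, SDBG, CV and MAGE estimate the effect of replacing breakfast. If those days come after stopping, the same changes estimate persistence. A mixture would give a weighted average. A reader who cannot tell which applies could misread the result, a null result above all. Visit 4 also cannot be after the intervention if the CGM that begins there lies wholly within it.

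Second, the measurements paragraph puts 2h-PG at visit 4, while the only final glucose tolerance test is at visit 5. Taken literally, the analysis needs a value at a visit where no such test is described.

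**Working it through.** **Inputs** (all from the Study Protocol section): baseline CGM 72 h = 3 days, visit 2 to visit 3; randomisation at visit 3; intervention 4 weeks = 28 days; visit 4 on Day 29; visit 5 on Day 32; follow-up CGM 32 − 29 = 3 days. The Day-1 anchor is not in the readable text, so it is varied as an assumption.

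**Formulas.** Let *s* be the day number on which the regimen starts.

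- Days elapsed at visit 4 = 29 − *s*
- Days elapsed at visit 5 = 32 − *s*
- CGM days inside the 28 days = min(3, max(0, *s* + 28 − 29))

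| Assumed anchor | *s* | Days at visit 4 | Days at visit 5 | CGM days inside 28 |
|---|---|---|---|---|
| Visit 3 = Day 0 | 0 | 29 | 32 | 0 of 3 |
| Visit 3 = Day 1 | 1 | 28 | 31 | 0 of 3 |
| Visit 3 = Day 1, product from next day | 2 | 27 | 30 | 1 of 3 |
| Visit 2 = Day 0 | 3 | 26 | 29 | 2 of 3 |
| Visit 2 = Day 1 | 4 | 25 | 28 | 3 of 3 |

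**Do the plan's own figures reproduce?** Yes, in two ways. With visit 3 as Day 1, the 28 days are complete exactly at visit 4. With visit 2 as Day 1, visit 3 is Day 1 + 3 = Day 4, and the 28 days are complete exactly at visit 5.

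**Do the labels fit?** On the first reading they all do. The second CGM begins when the four weeks have ended, the visit-4 samples follow the intervention, and the follow-up values come after treatment. On the second reading the CGM closes the four weeks, and one label is loose: visit 4 is called post-intervention at 25 days, 3 days early.

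**Is there a contradiction?** One arises only if the CGM is also required to lie inside the 28 days, and no sentence requires that. Nor does any sentence say that the product stops at day 28. A result of 0 of 3 therefore means outside the stated four weeks, not shown to be off the product.

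**2h-PG.** The labels differ by 32 − 29 = 3 days under every anchor. A 2-hour value can come only from a tolerance test, and the text describes one final test. Each participant therefore has one follow-up 2h-PG value, and the schedule is written identically for both arms. The paired test and the comparison of changes use that same value whichever visit label is attached to it.

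**The case for a change.** The strongest case for acting is that the schedule figure cannot settle everything. It could fix the day count, but it could not make visit 4 post-intervention and also put the CGM that starts there inside the four weeks. That is correct. It bites only if the plan claims both, and it does not.

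A second argument is that regimen status could matter greatly. As an illustration, assume 80% power for breakfast AUCpp when all 3 days are on the regimen, an effect averaged over days, and a share *c* of the effect kept on off-regimen days. With *k* on-regimen days the retained effect is *f* = (*k* + (3 − *k*)*c*)/3, and power is Φ(2.8016*f* − 1.96) + Φ(−2.8016*f* − 1.96). For *k* = 3, 2, 1, 0 this gives 80%, 46%, 15%, 5% when *c* = 0, and 80%, 65%, 46%, 29% when *c* = 0.5. The arithmetic is right, but the starting power, the carry-over and the equal weighting of days are all assumed. The readable text gives no sample size, SD or effect size. The figures also treat days outside the 28 as days off the product, which the text does not say. They show that status affects interpretation; they do not measure a loss in this trial.

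A third argument is that an added rule would cost little: analyse on-regimen and after-stopping days separately, and report breakfast AUCpp apart from other meals. Nothing in the text suggests that status varies between days or participants, and the readable text describes no daily record of product use from which to make the split. AUCpp is already defined meal by meal, so a separate breakfast figure is a reporting preference.

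A fourth is that a fasting test at visit 5 could supply a second fasting sample for FPG, insulin and HOMA-IR. The measurements paragraph already assigns those to visit 4 after an overnight fast.

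What stands is that regimen status during the follow-up CGM is unwritten and affects how the result is described, and that the two sentences on 2h-PG disagree.

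**Conclusion.** No change to the analysis plan follows. The first part is a gap that those running the trial can fill from what they know of the schedule: whether participants were still replacing breakfast while the second sensor was worn. The same follow-up values and the same tests apply on either answer. Only the description of the CGM result differs, as an effect on the regimen or one after stopping. The comparison between randomised arms is sound in both cases, because both arms follow one schedule.

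The second part is a clerical slip. The measurements paragraph and the visit description must be reconciled on the visit for 2h-PG. This review takes no position on which schedule is right, and no bias between arms follows.

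The size is 0 to 3 of 3 CGM days inside the 28 days, depending on an anchor that the missing schedule figure may give, and a 3-day difference in the 2h-PG label. The effect on AUCpp, SDBG, CV and MAGE cannot be calculated from the documents. The conclusion assumes that the product was handled uniformly across participants during the follow-up CGM and that each participant had one final tolerance test. The text gives no reason to doubt either.

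### Do whole-day SDBG, CV and MAGE need a breakfast-excluded analysis because the intervention replaces breakfast?

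*Combined protocol and SAP*

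**What the plan says.** All of the following is in the Study Protocol section unless stated otherwise.

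- **Intervention.** "Participants in the study group were instructed to replace breakfast with Glucerna SR"; both groups received lifestyle education. Allocation is made at visit 3 and the assignment lasts 4 weeks.
- **First CGM.** Participants were "continuously monitored for 72 hours (visit 2 to visit 3", which is before randomisation.
- **Second CGM.** "At the end of the 4-week intervention, subjects underwent another CGM from visit 4 (Day 29) to visit 5 (Day 32"). The paragraph on anthropometric and biochemical measures labels visit 4 as following the intervention: "Anthropometric and biochemical parameters were measured at visit 1 (baseline) and visit 4 (post-intervention").
- **Variability outcomes.** "Intra-day glycaemic variability (GV) parameters include the standard deviation of blood glucose values (SDBG), glucose coefficient of variation (CV") and MAGE. The only filter is on size and applies to MAGE, which keeps excursions larger than "1 SDBG of the mean glycaemic values were considered for the calculation of MAGE". No meal window is excluded.
- **Post-meal outcome.** AUCpp is calculated separately for each meal, using a 4 h period.
- **Schematic.** "The schematic outline of study conduction is illustrated in the figure below". The figure is not reproduced in the text available.
- **Analysis.** The Statistical analyses section gives paired t tests within groups and Student's t tests on changes between groups. It describes no meal-specific comparison.

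**The concern.** The product replaces one meal, but SDBG, CV and MAGE pool the hours after that meal with the rest of the day. The baseline recording precedes randomisation, so its breakfasts are ordinary ones in both groups. If the study group was still taking the product on Days 29 to 32, the change from baseline compares ordinary breakfasts with product breakfasts. A fall in SDBG could then reflect the swap itself, with the other 24 − 4 = 20 hours unchanged. A reader might take the same fall as steadier glucose throughout the day, or as a benefit that outlasts the product.

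No visible sentence says which breakfast was eaten on those days, and no described analysis sets the breakfast hours aside. What is at stake is the label on three outcomes (on-intervention or after-intervention) and how far a finding can be generalised. The validity of the t test is not in question.

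A smaller matter sits alongside. The biochemical paragraph includes the 2-h OGTT glucose among measures taken at visits 1 and 4. The CGM paragraph places the last OGTT at visit 5: "at which a final OGTT in the fasting state was conducted".

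**Working it through.** The visible text gives no sample size, SD, target difference or power, so there is no planned figure to reproduce. Three checks can be made.

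**1. Do the dates settle the breakfast status?** Day 1 is not defined. If it is the day of randomisation (an assumption), 4 weeks × 7 = 28 days, so the assigned period covers Days 1 to 28 and the second CGM begins on the next day. That, together with the label on visit 4 and the before-and-after-treatment wording in the Statistical analyses section, leans towards the assigned period having ended. It does not establish what was eaten.

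**2. How much of the day is involved?** Reading the AUCpp definition as a 4 h post-meal window, the share is 4/24 = 16.7%. Over 72 h with three breakfasts it is 12/72, the same share. The 72 h figure is stated only for the first CGM.

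**3. How far could one meal move the outcomes?** Every shape input here is assumed:

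- readings every 5 minutes, base 6.5 mmol/L;
- meals at 07:00, 12:00 and 18:00;
- cosine-shaped excursions peaking 4 mmol/L above base at 1 h and back to base at 4 h;
- no background wave, and nothing changed except the breakfast peak.

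Each excursion averages half its peak over 4 h, so the daily mean is 6.5 + 3 × (4 × 0.5 × 4/24) = 7.5 mmol/L. SDBG is 1.417 mmol/L.

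| Breakfast excursion lower by | SDBG (mmol/L) | Change in SDBG | Mean (mmol/L) | Change in CV | MAGE (mmol/L) | Change in MAGE |
|---|---|---|---|---|---|---|
| 20% | 1.332 | −6.0% | 7.433 | −5.1% | (3.2 + 4 + 4)/3 = 3.73 | −6.7% |
| 40% | 1.271 | −10.3% | 7.367 | −8.7% | (2.4 + 4 + 4)/3 = 3.47 | −13.3% |
| 60% | 1.235 | −12.8% | 7.300 | −10.4% | (1.6 + 4 + 4)/3 = 3.20 | −20.0% |

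CV change is the SDBG ratio divided by the ratio of means; for example (1.235/1.417)/(7.300/7.5) − 1 = −10.4%. MAGE is taken as the mean of the pre-meal-to-peak rises above 1 SDBG.

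The result depends heavily on the assumed curve:

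- With no background wave, other-meal peaks of 2 to 6 mmol/L and a breakfast peak 0.7 to 1.5 times the others, SDBG changes by −25% to −3%.
- Add a 24-h wave whose peak-to-trough height is half the other-meal peak. Cresting at 04:00 to 06:00, it takes the largest fall in SDBG to about 31%. Cresting at 20:00, it gives SDBG −12.4% to +2.0% and CV −10.5% to +4.8%.
- MAGE can rise. With breakfast at 0.7 of the other peaks and 60% lower, its excursion is 2.8 × 0.4 = 1.12 mmol/L, below the SDBG of 1.23. It drops out, and MAGE goes from (2.8 + 4 + 4)/3 = 3.6 to 4.0, up 11%.

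Removing the 4 h after breakfast leaves SDBG and CV unchanged in this model, but only because each excursion is made to end at 4 h. Curves with a longer tail leave −0.3% to −1.6% in SDBG. If the product was not taken on the CGM days, the direct effect is zero for all three outcomes.

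**The case for a change.** The best case for acting is that clarity is cheap. The CGM data exist, AUCpp already requires meal times, and a reader shown a lower SDBG will tend to read it as a whole-day improvement. One sentence on breakfast status and one supportive recalculation would show whether variability changed outside the replaced meal. The arithmetic supports the premise: if the product was in force, one meal can move SDBG by an amount that matters.

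Part of this stands. The visible text is silent on breakfast during the second CGM, the meaning of the outcomes depends on it, and a report of the trial should state it.

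The rest does not carry a change. The schematic of study conduct may hold the answer, and its absence from the extracted text is not a defect of the plan. The recalculation corrects no rule or claim in the plan. It is poorly defined for MAGE, because cutting out 4 h breaks the sequence of peaks and nadirs and shifts the 1-SDBG threshold. It also could not tell a same-day effect on later meals from a lasting one. Nor does AUCpp offer the contrast it seems to: it is calculated per meal, but no comparison by meal is described.

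**Conclusion.** No change to the plan is called for. The groups are randomised and have the same CGM schedule, so Student's t test on the change in whole-day SDBG, CV or MAGE is a fair comparison whether or not the product was taken on Days 29 to 32. In the first case it estimates variability on the product; in the second, variability after it. Both are sensible questions, and the plan calls the measures intra-day without claiming more.

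The open detail is descriptive. The sponsor knows the schedule and can label the outcomes in the report, if the schematic does not already do so. A breakfast-excluded SDBG or CV is an option for exploration, not a correction.

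No single percentage should be attached to the point. The direct effect is zero if the product had stopped. If it had not, the central illustration gives SDBG 6.0% to 12.8% lower, but all curve inputs are assumed and other plausible inputs change the size and even the sign.

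The visit for the final 2-h OGTT glucose is a clerical slip: the two paragraphs must be reconciled, and it has no bearing on the variability outcomes.

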### **Statistical analyses**

Continuous variables at baseline were compared between the two groups by Student's *t* test. Comparison of categorical variables between groups was performed by  $\chi^2$  tests. Differences in the parameters before and after treatment were analysed by paired *t* test. The changes ( $\Delta$ ) in variables were compared with Student's *t* test. Statistical analyses were performed using SPSS software version 17.0 (SPSS Inc., Chicago, IL, USA). A *P* value of  $< 0.05$  (two-tailed) was considered statistically significant.

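### Do the before/after paired t tests let shared change pass as a product effect?

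*Combined protocol and SAP*

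**What the plan says.** The Statistical analyses section lists its tests in sequence. For pre/post comparison it says "Differences in the parameters before and after treatment were analysed by paired *t* test". It does not state whether this is done within each group or on all participants together; within each group is the natural reading. The next sentence gives the comparison between groups: the changes "in variables were compared with Student's *t* test". A single two-sided 0.05 threshold closes the section and covers all tests, including the baseline comparisons. The text supplied names no primary analysis and does not rank the tests.

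Three design features in the Study Protocol section bear on the point:

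- **Randomisation:** "the subjects were randomized (1:1) to receive either study group or control group for 4 weeks".
- **Shared co-intervention:** "both groups received lifestyle education".
- **Order of screening:** "each subject underwent a 75-g oral glucose tolerance test (OGTT). Participants who met the eligibility criteria were then continuously monitored". Visit 1 is also the baseline for the biochemical measures, including fasting and 2-hour plasma glucose. The baseline CGM period runs from visit 2 to visit 3, after eligibility is settled. The eligibility criteria are not in the text supplied.

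**The concern.** A mean change within one group mixes any product effect with everything else that moves the measurement over four weeks. Two such influences are visible here. Both groups are taught about lifestyle, so both may improve. And if participants were kept because of a raised visit 1 glucose, later values would on average be lower without any treatment.

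A paired t test responds to all of this. Read alone, a significant fall in the study group could be credited to the product when the two groups do not differ. A subtler error is to note that the study group changed significantly and the control group did not, and to treat that contrast as a test of the difference. If conclusions rested on either reading, the false-positive rate would be far above 5% and the randomisation would go unused.

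**Working it through.** The documents give no sample size, standard deviation or effect size, so there is no stated figure to reproduce. Group sizes, shared changes, correlations and cut-offs below are assumptions. The 0.05 two-sided level and 1:1 allocation come from the plan.

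**1. What each test estimates.** Let L be the shared education and time effect, R the regression to the mean, and τ the product effect.

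- Expected change, study group: L + R + τ
- Expected change, control group: L + R
- Difference between groups: (L + R + τ) − (L + R) = τ

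The paired test in the study group targets L + R + τ. The planned t test on the changes targets τ alone. Selection precedes randomisation at visit 3, so R has the same expectation in both groups.

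**2. Shared change, τ = 0.** With n per group and a shared change of d standard deviations of the change, the paired test's rejection probability p comes from the noncentral t distribution with n − 1 degrees of freedom and noncentrality d√n. The probability that exactly one group is significant is 2p(1 − p); that only the study group is, p(1 − p). The between-group test was simulated with 40,000 trials per row.

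| n per group | d | p, paired | Exactly one group | Study group only | Between-group test |
|---|---|---|---|---|---|
| 15 | 0.3 | 19.2% | 31.0% | 15.5% | 4.9% |
| 30 | 0 | 5.0% | 9.5% | 4.8% | 5.1% |
| 30 | 0.3 | 35.5% | 45.8% | 22.9% | 5.1% |
| 30 | 0.5 | 75.4% | 37.1% | 18.6% | 5.0% |
| 50 | 0.5 | 93.4% | 12.3% | 6.2% | 4.9% |

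For example, at n = 30 and d = 0.3: 2 × 0.355 × 0.645 = 0.458. The largest possible value is at p = 0.5: 2 × 0.5 × 0.5 = 50%, or 25% for the study group alone.

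**3. Regression to the mean, τ = 0.** For selection above a cut-off z (in SD of the screened population) and test-retest correlation ρ, the expected fall is (1 − ρ) × φ(z) / (1 − Φ(z)).

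- ρ = 0.8, z = 0: 0.2 × 0.798 = 0.16 SD
- ρ = 0.5, z = 0: 0.5 × 0.798 = 0.40 SD
- ρ = 0.5, z = 0.5: 0.5 × 1.141 = 0.57 SD

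Simulated rejection rates (10,000 trials each):

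| ρ | z | Paired, n = 15 / 30 / 50 | Between-group, n = 15 / 30 / 50 |
|---|---|---|---|
| 0.8 | 0 | 15.8% / 27.9% / 44.2% | 4.6% / 5.0% / 5.0% |
| 0.5 | 0 | 35.0% / 63.2% / 85.7% | 5.2% / 4.8% / 5.0% |
| 0.5 | 0.5 | 62.6% / 91.8% / 99.2% | 5.2% / 5.1% / 4.9% |

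**4. Which outcomes this reaches.** Regression to the mean of this kind applies directly only to measures used for selection, plausibly the visit 1 glucose values, and more weakly to measures correlated with them. The CGM measures have a baseline recorded after eligibility, so the mechanism is much less direct there. With the criteria unseen, neither its size nor its direction is known; the table models lower cut-offs only.

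**5. What removing the P value would change.** A 95% t interval for the mean change excludes zero exactly when the paired test gives P < 0.05. Replacing one with the other alters the display, not the information.

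**The case for a change.** The best argument for a change is that the plan never says which test governs. Both fall under the same threshold and no primary analysis is named. If the study group shows a significant fall and the between-group test does not, nothing in the text rules out leaning on the former. One sentence would close that route at almost no cost.

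The silence is real, and so is the statistical principle. But the 0.05 sentence is a general convention that also covers the baseline t tests and χ² tests; it gives no test priority for inference. The percentages for significance in one group only are error rates of a decision rule found nowhere in the plan. In a 1:1 randomised trial with a planned comparison of changes, a competent analyst takes that comparison as the evidence on the product and the paired results as description. A report that did otherwise would be misreading its own analyses; that is a fault to raise against the report.

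**Conclusion.** The concern does not call for a change. The paired tests cannot isolate a product effect, and under assumed inputs they can be significant in about 16% to 99% of trials through regression to the mean alone. The plan does not depend on them for that purpose. Its own test of the changes between randomised groups removes shared influences in expectation and rejected in 4.6% to 5.2% of null trials across the simulated scenarios. Followed as written, the plan yields a valid comparison between groups. Stating that this comparison carries the conclusion would be a harmless clarification that leaves every estimate and P value as it is. This rests on the planned t test of the changes being a comparison between the two groups, which the wording and the two-group design support, and on randomisation following selection, which the Study Protocol section states.

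### Treatment effects on continuous outcomes are tested only by an unadjusted t test on change; using the pre-randomisation baseline as a covariate would usually give more precision at no cost

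*Combined protocol and SAP*

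**What the plan says.** The Statistical analyses section names four procedures.

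- Baseline balance: "Continuous variables at baseline were compared between the two groups by Student's *t* test".
- Categorical variables: chi-square tests.
- Before versus after treatment: "Differences in the parameters before and after treatment were analysed by paired *t* test".
- Change from baseline: the changes "in variables were compared with Student's *t* test".

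Only the last can estimate a treatment effect on a continuous outcome. The first concerns values before treatment, the second does not apply to continuous data, and the third compares times rather than groups. The sentence on changes does not name the groups, but an unpaired test on changes has no other sensible reading. No ANCOVA, regression or mixed model appears anywhere.

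The Study Protocol section fixes when the baselines were taken.

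- OGTT: "Following study enrolment (visit 1), each subject underwent a 75-g oral glucose tolerance test (OGTT".
- Laboratory and anthropometric measures: "Anthropometric and biochemical parameters were measured at visit 1 (baseline) and visit 4 (post-intervention".
- CGM: "Participants who met the eligibility criteria were then continuously monitored for 72 hours (visit 2 to visit 3".
- Randomisation: "After 3 days of CGM (visit 3), the subjects were randomized (1:1".

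Every repeated outcome therefore has a baseline that treatment cannot have affected. For AUCpp, SDBG, CV and MAGE it is the CGM between visits 2 and 3. For the OGTT, laboratory and anthropometric measures it is visit 1.

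**The concern.** Subtracting the baseline is adjustment with the slope of follow-up on baseline fixed at 1. The slope that minimises the variance is rho × SD(post)/SD(baseline), which is below 1 whenever the two SDs are similar and the correlation is imperfect. Fixing the slope at the wrong value leaves baseline noise in the estimate, so standard errors are larger and power is lower than the same participants could give.

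A second consequence follows. The plan tests for baseline differences but has no means of allowing for one. If the arms differ by chance at baseline, the change-score estimate in that trial is shifted, against the direction of the imbalance when the slope is below 1. Over repeated randomisations the shifts average to zero and are already part of the standard error, so this is not a systematic bias. ANCOVA removes it all the same.

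**Working it through.** **Inputs.** From the documents: Student's t test on change, two-sided 5% level, 1:1 allocation, baselines before randomisation. The documents state no sample size, power, effect size, SD or correlation, so there is no figure of the plan's own to reproduce. Assumed: rho (baseline to follow-up correlation) of 0.3 to 0.9, and k = SD(post)/SD(baseline) of 0.8, 1 or 1.25. Both may differ by outcome.

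**Variances.** In units of the baseline variance, and up to a common factor that depends on the arm size:

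- Var(change) = 1 + k² − 2·rho·k
- Var(ANCOVA) = k²(1 − rho²)
- Difference = 1 − 2·rho·k + rho²k² = (1 − rho·k)²

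The difference is a square, so it is never negative, and it is zero only when the slope rho·k equals 1. At k = 1 the ratio simplifies to (1 − rho²)/[2(1 − rho)] = (1 + rho)/2.

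**Power.** If the change-score test has 80% power, its non-centrality is 1.96 + 0.84 = 2.80. ANCOVA power is then Φ(2.80/√ratio − 1.96). For example, at rho = 0.5 and k = 1: 2.80/√0.75 = 3.23, 3.23 − 1.96 = 1.27, and Φ(1.27) = 0.90.

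| k | Result | rho 0.3 | rho 0.5 | rho 0.7 | rho 0.9 |
|---|---|---|---|---|---|
| 1 | variance ratio | 0.65 | 0.75 | 0.85 | 0.95 |
| 1 | power | 93.5% | 90% | 86% | 82% |
| 1.25 | variance ratio | 0.78 | 0.89 | 0.98 | 0.95 |
| 1.25 | power | 89% | 84% | 81% | 82% |
| 0.8 | variance ratio | 0.50 | 0.57 | 0.63 | 0.61 |
| 0.8 | power | 98% | 96% | 94% | 95% |

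At k = 1.25 and rho = 0.8 the slope is 1.25 × 0.8 = 1 and there is no gain.

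**Interval width.** Width scales with √ratio. At k = 1 the ANCOVA interval is narrower by 1 − √0.75 = 13% at rho 0.5, 1 − √0.85 = 8% at rho 0.7 and 1 − √0.95 = 3% at rho 0.9.

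**Small arms.** Estimating the slope multiplies the ANCOVA variance by 1 + 1/(2n − 4) for n per arm.

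- At rho 0.9 and k = 1: 0.95 × (1 + 1/16) = 1.01 for n = 10, 0.95 × (1 + 1/36) = 0.98 for n = 20, and 0.95 × (1 + 1/56) = 0.97 for n = 30.
- With non-central t power (2n − 2 degrees of freedom for change, 2n − 3 for ANCOVA), a change-score power of 80% becomes 93%, 89%, 85% and 81% at n = 20 for rho 0.3, 0.5, 0.7 and 0.9.
- At n = 10 it becomes 92%, 88%, 83–84% and 79%.

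**Simulation.** Over 40,000 trials per scenario (normal data, equal SDs, 10 to 100 per arm), type I error was 4.7–5.2% for the change test and 4.8–5.1% for ANCOVA. Mean estimates under the null were within 0.005 SD of zero for both, and the variance ratios matched the formula.

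**Chance imbalance.** Given a baseline difference d between arms, the change-score estimate shifts by (rho·k − 1)·d. For d = +0.3 baseline SD and k = 1 the shift is −0.7 × 0.3 = −0.21, −0.5 × 0.3 = −0.15, −0.3 × 0.3 = −0.09 and −0.1 × 0.3 = −0.03 SD for rho 0.3, 0.5, 0.7 and 0.9.

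**The case against.** The strongest reply is that this is a choice of estimator, not an error. The change-score test is valid, already uses each participant's baseline by subtraction, and contradicts nothing in the documents. That is true, and it limits the point to precision.

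The size of the loss here is also unknown. The assumed range runs from half the variance (k = 0.8, rho 0.3), through no gain (k = 1.25, rho 0.8), to a slight loss (10 per arm, rho 0.9). The largest gains need the SD to fall by 20% at follow-up, which nothing in the documents supports. This stands too: the algebra is certain, the practical importance is not.

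Eligibility was applied after the visit 1 OGTT. If the criteria restrict OGTT glucose (an assumption; the criteria are not shown), the baseline spread of FPG and 2h-PG is narrower, and so is the gain. The slope and residual variance do not change, but the part that ANCOVA removes, (1 − slope)² × Var(baseline), shrinks. With baseline variance halved:

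- At slope 0.5 the ratio is 0.75/(0.75 + 0.25 × 0.5) = 0.86, so the saving falls from 25% to 14%.
- At slope 0.7 it is 0.51/(0.51 + 0.09 × 0.5) = 0.92, so the saving falls from 15% to 8%.

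This is a fair caution for the OGTT outcomes. It does not apply directly to the CGM measures.

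Finally, the text is in the past tense ("Statistical analyses were performed using SPSS software version 17.0"), so the analysis may already have been done. In that case ANCOVA can no longer be prespecified. None of these points gives a reason to prefer the change score, because the better analysis uses data already collected.

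**Conclusion.** The point holds as a free improvement in precision, not as a flaw that invalidates results. The one between-group test on continuous outcomes leaves a pre-randomisation baseline unused as a covariate. In large samples this can only lose precision or leave it unchanged. With equal SDs and correlations of 0.5 to 0.7, ANCOVA would save 15–25% of the variance; at 0.9 it would save about 5%, and in arms of about 10 it would save nothing. These figures rest on assumed correlations and SD ratios, and on a linear relation with the same slope in both arms.

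**What to change.** Replace the sentence on comparing changes with: *Between-group effects on continuous outcomes are estimated by ANCOVA of the post-intervention value on randomised group and the participant's own baseline value, and reported as an adjusted mean difference with 95% CI.* The baseline is the CGM between visits 2 and 3 for the CGM outcomes and visit 1 for the others.

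If the change-score analysis has already been run, keep it, report ANCOVA beside it, and state that ANCOVA was added post hoc.

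The cost is one sentence and one degree of freedom per outcome, with no new data. The confidence interval is a small reporting addition, since the plan gives only a P value threshold.
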